Retention and Adherence

Based upon our past experience with clinical trial and prospective cohort studies of diverse populations (R01 DA025078; N01 HC48049), we expect at least a 60% participation rate across the four surveys. In our recent smoking cessation trial,⁹⁴ of the 1,989 sessions scheduled for the 259 participants at the Northwestern clinical site over their first 6 months, 1,604 (81%) were completed.

To maximize enrollment in this study, we will:

- 1) Target patients who are most likely to view one of the NNHSC clinical sites as their medical home through defining eligibility based in part on at least one clinic visit during the past year;¹⁰⁷
- 2) Include monetary compensation for each survey completion, plus \$50 for completing the in-person session at week 28 (original timeline) or week 14 (alternative shorter timeline);¹⁰⁷ and
- 3) Develop and implement strategies to engage the NNHSC community.^{108,109} Drs. [name] and [name], along with [name], will provide critical guidance on best practices and issues of cultural competency related to research targeting low-income and African American populations.^{110,111} For example, we plan to conduct a clinic-wide outreach campaign across the seven participating NNHC clinics to increase interest in the health habits survey. Additionally, we will use small, low-cost giveaways to increase recognition of the survey once research assistants because to recruit and enroll patients.

We have developed a plan to maximize retention of participants to overcome follow-up challenges that are often experienced in longitudinal studies of low-income populations,¹¹²⁻¹¹⁴ such as residential instability. Strategies will include the following:

- 1) A user-friendly electronic tracking database of participants;
- 2) Elicitation at baseline and every follow-up session of relative and (or) neighbor contacts to locate participants if needed;
- 3) Research personnel training on team building and positive attitudes;
- 4) Flexible scheduling of telephone sessions, including Saturday appointments;
- 5) Sending personalized reminder cards and retention items (i.e., water bottles, draw string bags, earbuds, T-shirts);
- 6) Reminder letters with small giveaway items sent one week prior to their scheduled session and reminder calls to participants 1-2 days prior to their scheduled session
- 7) Establishing strong rapport with participants by providing a friendly experience during assessments;

PROTOCOL SHORT TITLE: Choose to Change – Reducing Tobacco Disparities

- 8) Sending seasonal newsletters about living a healthy lifestyle;
- 9) Demonstrating a positive and caring attitude towards participants¹⁰⁹;
- 10) Rapid rescheduling of missed appointments; and
- 11) Acknowledgement and appreciation of participant effort.

These enrollment and retention strategies have been effective in pragmatic clinical trials and community studies of underserved populations,¹¹²⁻¹¹⁵ as well as in our ongoing cohort study (N01 HC48049).

STATISTICAL ANALYSIS PLAN

Power

To address power for hypotheses related to **Aim 1 (Treatment Engagement at 6 Weeks)**, we base our estimates for the proportion of participants completing a Quitline session by 6 weeks in the Choose to Change condition on our pilot study that resulted in a **24%** engagement rate. As for the Usual Care condition, we expect that current NNHSC Ask, Advise, Refer practice involving the Quitline as the primary referral program will result in a tripling to **10%** of the 3.3% engagement rate achieved in our EHR fax-referral project, in which our NIH-funded study of long-term nicotine patch treatment, with inclusion and exclusion criteria, served as the primary referral program.⁹⁴ Assumed rates by condition for each of the three outcomes of interest and participants per condition are presented in Table 3. We propose that a minimum of N=265 independent participants be randomized to Choose to Change versus N=265 to Usual Care, for a total N=530. Such a 1:1 allocation ratio guarantees **99% power** for the comparison of Choose to Change versus Usual Care at two-sided alpha=.05. This sample size requirement equates to 40 participants per month over the 15-month randomization period. In our three-week pilot study, 132 patients were processed through the workflow in Figure 3, a rate of 175 per month.

Table 3. Assumed Intent-to-Treat Rates by Condition for the Three Outcomes of Interest and Participants per Condition

Study Aim	Usual Care	Choose to Change
Aim 1: Engagement (6 Weeks)	10%	24%
Aim 2: Utilization (12 Weeks)	7%	15%
Aim 3: Cessation (26 Weeks)	2%	7%
Participants	265	265

Our power estimates for **Aim 2 (Treatment Utilization at 14 Weeks)** will be based on Williams et al.⁹ who reported a 30% utilization rate for combined counseling and medication at a later time point than ours (6 months), following a face-to-face SDT-based intervention. Assuming 6-month utilization rates (one or more counseling calls after the initial counseling call) for the Usual Care and Choose to Change conditions of **7%** and **15%**, respectively, would be consistent with their treatment utilization odds ratio of 2.38 (95% CI=1.67-3.39), albeit at a lower baseline rate than they report. Our proposed randomization plan guarantees **84% power** for the comparison of Usual Care versus Choose to Change at two-sided alpha=.05.

Our power estimates for **Aim 3 (Smoking Cessation at 28 Weeks)** will be based primarily on Rigotti et al.²⁷ who reported 7-day point-prevalence abstinence rates at 14 weeks of 1% for standard care and 5% for population mail outreach under an Intent-to-Treat (ITT) approach. We expect that these 12-week ITT rates will rise to 3% in our Usual Care condition and 10% in the Choose to Change condition. Even if these rates then drop to **2%** in our Usual Care and **7%** in Choose to Change at 26 weeks, we still have **80% power** for the comparison of Choose to Change versus Usual Care at two-sided alpha=0.05.

Data Analysis

All outcomes of interest for **Primary Aims 1-3** are binary (treatment engagement, treatment utilization, smoking cessation) and can be analyzed using logistic regression methods. Analyses will be conducted first using an ITT principle (missing=treatment failures). We will also conduct an adherence sample analysis that includes only participants reached at the 28-week follow-up ($\geq 75\%$ of the sample based on our experience). This approach addresses the question of effectiveness more directly, but it is subject to more bias if attrition is large or differential by treatment condition. Therefore, we will complement it by analysis of non-response patterns using sociodemographic (age, gender, race, ethnicity, marital status, household income, education), and healthcare (time since last clinic visit, type of health insurance) characteristics. These can be used to create propensity scores that allow for inverse-probability-weighting (IPW) of observed outcomes^{116,117} to achieve balance across potential confounders of the treatment-to-outcome relationship. Ideally, the distribution of propensity scores will show large overlap across study conditions. If not, that will be taken as evidence that completers are not comparable on measured confounders across conditions, and that one should refrain from

PROTOCOL SHORT TITLE: Choose to Change – Reducing Tobacco Disparities

further comparisons. PROC GENMOD of SAS/STAT 9.2¹¹⁸ can handle subject-level probability weights. Similar findings across all three approaches would increase confidence in the results overall. Both raw and adjusted rates will be presented for each outcome by study condition. For the cessation outcome, we will also explore the impact of smoking history (e.g., past year quit attempts, past referral for Quitline treatment), race, and gender on non-response. We will also use propensity score modeling to examine the relationship between treatment utilization at 14 weeks and abstinence at 28 weeks. Since available data indicate little effect of NRT type on outcome, we will model NRT dose/duration, while controlling for patterns of utilization.

Exploratory Aim 1 (Moderators of Choose to Change Effects). We will focus our search for moderators on baseline variables such as readiness to quit, health literacy,⁷¹ smoking level, time since the patient's last clinic visit in which smoking was addressed, and recent smoking reduction.⁵³ Participants who smoke more than 10 cigarettes per day, who have recently attempted to reduce their smoking, and those lower on motivational readiness to quit are expected to be disproportionately responsive to Choose to Change intervention. In addition, participants with lower literacy and those with a more recent clinic visit during which smoking was addressed are expected to be especially likely to benefit. These factors are expected to be especially responsive to the person-centered and the low-income targeted elements of the Choose to Change intervention (Figure 2), though we realize that there may be other potential moderators. Other variables to be explored as potential moderators include initial choice of smoking cessation versus reduction, and race/ethnicity. Analysis will be conducted using logistic regression, with a separate model for each outcome variable. The predictor variables will include treatment condition, the moderator variables, and their two-way interactions with condition. Sociodemographic (e.g., gender), psychosocial (e.g., perceived stress), and smoking (e.g., menthol cigarette use) variables known to influence smoking cessation will serve as covariates.

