PROTOCOL SHORT TITLE: Choose to Change – Reducing Tobacco Disparities

Protocol Title: **Reducing Tobacco Use Disparities Among Adults in Safety Net Community Health Centers**

Principal Investigators: [name]. (Lead PI)
Northwestern University
[contact]
[contact]

[name]. (Co-PI)
University of Illinois at Chicago
[contact]

[name]. (Co-PI)
Northeastern Illinois University
[contact]

[name]. (Site PI)
Near North Health Services Corporation
[contact]

[name]. (Site PI)
Alliance of Chicago

Biostatistician: [name].
Brown University
[contact]

Version Date: May 14, 2018

ClinicalTrials.gov
Registration Number: NCT03077737

PURPOSE OF STUDY & OBJECTIVES

An estimated 26 million smokers still receive no treatment for their smoking during their primary care visits. Given the persistent clinical system, provider, and patient barriers to addressing smoking, especially among poor populations, an EHR-automated population health management approach that links a healthcare system with community services both clinically and electronically to engage all smokers may increase access to effective treatment. Increased access is especially significant for low-income smokers who are underserved and carry a disproportionate burden of tobacco-related disease. This 2-group randomized controlled trial will evaluate the effectiveness of a person-centered population health management intervention for smoking cessation in low-income smokers. The following aims and hypotheses will be tested:

Primary Aim 1 (Effect on Treatment Engagement): Compare Choose to Change versus Usual Care for engaging low-income smokers in treatment. Hypothesis: Choose to Change will increase the proportion of smokers who complete a behavior counseling call by 6 weeks (24%), compared with Usual Care (10%).

Primary Aim 2 (Effect on Treatment Utilization): Compare Choose to Change versus Usual Care for increasing treatment utilization. Hypothesis: Choose to Change will increase the proportion of smokers who complete ≥ 1 additional behavior counseling calls by 14 weeks (15%), compared with Usual Care (7%).

Primary Aim 3 (Effect on Smoking Cessation): Compare Choose to Change versus Usual Care for increasing smoking cessation. Hypothesis: Choose to Change will increase the proportion of smokers

PROTOCOL SHORT TITLE: Choose to Change – Reducing Tobacco Disparities

abstinent at 28 weeks (7%), as defined by bio-verified 7-day point-prevalence abstinence, compared with Usual Care (2%).

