Secondary Aim 1 (Cost Evaluation): Conduct a cost-analysis to determine the cost of providing effective cessation therapy to smokers using this letter-enhanced EHR-referral and outcomes system. Evaluate the cost effectiveness of the Choose to Change letter and automated /text messages compared to usual care by calculation the cost-effectiveness ratio as the average dollars spent per successful quit.

Exploratory Aim 1 (Moderators of Intervention Effects): Evaluate motivation to quit, time since last clinic visit during which smoking was addressed, health literacy, cigarettes per day, recent smoking reduction, initial choice of cessation versus reduction, race/ethnicity, and primary language as moderators of effect of Choose to Change on treatment engagement, treatment utilization, and smoking cessation.

Exploratory Aim 2 (Mediators of Intervention Effects): Evaluate change in perceived autonomy support, autonomous motivation, confidence in ability to quit, and attitude towards NRT as mediators of intervention effects on treatment engagement, utilization, and cessation.

BACKGROUND AND RATIONALE FOR STUDY

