Alternative study timeline: Due to funding constraints, participants enrolled February 2018 or after will be involved in study-related activities for about 4 months (18 weeks) from initial enrollment in the observational study and baseline assessment (week -4) through a final follow-up at week 14. Participants enrolled in this alternative study timeline will complete three phone-based assessments (Baseline/Week -4; Week 6; Week 14) and those who report abstinence from cigarettes at the Week 14 phone interview will be invited to come in for an in-person clinic visit within 2 weeks of their Week 14 phone session in order to bioverify smoking status. Randomization to treatment arm and all other study procedures will be conducted in the same way as for the participants completing the full 32 week study timeline.

Study Timeline

Development of Bilateral EHR Interface with the Quitline. Led by Drs. [name] and [name], we will complete the testing and refinement of the bilateral EHR interface between NNHSC and the Quitline. Trainings with providers in use of the new EHR functionality will also be conducted. The integration of NNHSC and the Quitline will enable the NNHSC study care coordinator and providers to make a one-step referral to the Quitline. In turn, the Quitline will communicate patient outcomes directly to NNHSC via the EHR. The existing EHR content will be modified to automate obtaining and documenting provider approval of patient involvement and generating and documenting the mailing of the intervention letters. All clinical information will be communicated to the Quitline using Health Level Seven (HL7) standards. The Quitline will use a HL7 interface engine to receive and “translate” the information within its secure network.

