For those randomized to the CtC intervention group, the CtC letter, electronically signed on behalf of [name] of NNHSC, will be created by the EHR system on NNHSC letterhead and mailed by the care coordinator or research assistant. One day after CtC letter mailing, the first CtC text message will be sent to notify CtC participants of the coming letter. The remaining 4 text messages will be sent per the timeline described above. After a 12-day participant opt-out period (described in the letter), names and contact details, including best times to be called, will be sent by the EHR referral system to the Quitline at 7:00pm each day a referral is made. Participants will be called within two days of referral. NNHSC and each of its clinics will have a unique code that will be sent via the EHR system to the Quitline along with an encrypted referral file of Choose to Change participants. A different code, but unique to NNHSC, will be used to identify and track outcomes for Usual Care participants. All codes will be specific to this study. They will serve to identify the study protocol: cessation-focused counseling and NRT or reduction-refocused counseling and NRT as a first step to smoking cessation. Once reached by the Quitline, the participant's referral data will be shown on one screen and the study protocol via the virtual library will be shown on a second screen. The protocol description and required data fields will ensure that participants are provided reduction-focused counseling if chosen, free NRT if willing and deemed safe, and that additional project-required data are collected. Patient-specific outcomes will be transmitted to NNHSC at the end of each day.

Proactive Quitline Treatment for Choose to Change and Usual Care Conditions

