Participants in both treatment conditions will have the opportunity to receive the same proactive Quitline treatment consisting of person-centered behavior counseling and NRT. The Quitline protocol relies on treatment determined to be effective in the 2008 U.S. PHS Clinical Practice Guideline.⁵ Participants who are reached and who accept treatment will first be asked for basic sociodemographic and smoking information. After registration and brief assessment, either smoking cessation- or reduction- focused treatment will be delivered depending on patient preference. Participants who choose reduction as their initial treatment goal will be guided toward setting a quit date aided by NRT. For all participants who engage in treatment, a self-help packet (Quit-Kit) will be mailed to provide written information on the topics covered during the initial phone session. Most calls last about 30 minutes, with the behavior counseling portion lasting about 15 minutes. A free 8-week course of NRT (patch, gum, or lozenge) will be mailed in two week allotments to participants who are willing to set a quit date and interested in and eligible to use NRT (i.e., free of medical contraindication). Per Quitline policy for Chicago residents, NRT is offered at no cost for uninsured residents and reduced cost for those who have Medicaid insurance. Because free NRT increases use of quitline treatment,^{46,104} NRT will be made available at no cost to all participants to eliminate differential cost by insurance type as a potential confounder of intervention effects.

If a participant is reached by the Quitline counselor but has not received the Choose to Change letter, smoking cessation or reduction treatment will be offered and delivered according to the participant's preference. For participants not reached during the first call attempt, the Quitline counselor will make two more calls in the following two days. A voice message will only be left if the voicemail inbox belongs to the referred participant. If three calls are made without a response, the outreach process will end. The Quitline counselor will either call at times designated by the participant to be convenient or at varying times during the day. The Quitline provides services seven days per week, from 7:00 AM through 11:00 PM.

MEASURES

EHR Characterization of Population

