Treatment engagement will be measured at 6, 14, and 28 (as applicable) weeks after letter mailing, and operationalized as the proportion of participants who accept the proactive Quitline call and accept treatment as defined by completing the counseling session. Participants who return a Quitline call and accept treatment also will be counted as having engaged in treatment. Further, we will assess: 1) the proportion of smokers who request cessation versus reduction counseling; and 2) the proportion of smokers who engage in treatment and who request NRT and (or) schedule a follow-up (proactive or reactive) counseling call.

Treatment utilization will be measured at 6, 14, and 28 (as applicable) weeks and will be defined as the proportion of participants who complete ≥ 1 additional counseling calls and receive and use NRT. The frequency and duration of sessions will also be measured.

Smoking cessation at 6 and 14 weeks will be defined as self-reported abstinence (not even a puff of a cigarette) for ≥ 7 days. At 28 weeks, breath CO will be used to verify abstinence for participants in the original study timeline. For participants in the alternative shorter study timeline, breath CO will be measured at 14 weeks to verify abstinence. Participants will be classified as abstinent if they report not smoking (not even a puff of a cigarette) for ≥ 7 days and have a CO ≤ 8 parts per million (ppm). Participants will be assumed to be smoking if they report smoking, cannot be reached to provide data, fail to provide a breath sample, or provide a breath sample that is >8 ppm.¹⁰⁵ Participants who report abstinence at 28 weeks (original timeline) or 14 weeks (alternative shorter timeline) will be invited for an in-person visit for breath carbon monoxide (CO) measurement to bio-verify abstinence status.

Moderators, Mediators, and Covariates

Hypothesized moderators of Choose to Change effects will be measured at baseline and include readiness to quit smoking,^{96,97} recent smoking reduction,⁵¹ cigarettes per day, time since last clinic visit during which smoking was addressed, initial choice of cessation versus reduction, race/ethnicity, perceived stress, , and discrimination. Hypothesized mediators of intervention effects on treatment engagement, utilization, and cessation will be measured at each survey time point and will include perceived autonomy support, autonomous motivation, confidence in ability to quit, and attitude towards NRT.

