[name] (UIC Co-PI) and [name] (UIC Co-I) contribute their expertise in community-based participatory research in smoking cessation among low-income and disenfranchised populations, and [name], specifically, designed our recruitment and retention plan. [name] (NEIU Co-PI) will be leading the cost evaluation component of the study.

Alliance of Chicago will provide research and EHR technical expertise for NNHSC's EHR (i.e., Alliance will build the e-Referral, e-Outcomes and letter components of the Choose to Change intervention within NNHSC's EHR.

PROTOCOL SHORT TITLE: Choose to Change – Reducing Tobacco Disparities

The Illinois Tobacco Quitline will provide their evidence-based cessation treatment to all participants who accept the referral and proactive call from the Quitline counselors. The Quitline staff will conduct the same counseling to study participants that they do to any other caller or patient referred for services. They will also electronically send the treatment outcomes information to the NNHSC EHR for all participants who complete Quitline counseling sessions.

All partners, academic and community-based, will be provided with a current IRB-approved protocol. As all staff conducting the research activities are NU staff, we hold regular weekly meetings to ensure successful coordination of these activities and ongoing research protocol monitoring.

Community-Based Participatory Research

The Choose to Change intervention has benefitted from six-year collaboration with NNHSC, including Winfield Moody Health Center, Alliance, and the Illinois Tobacco Quitline. NNHSC providers and patients guided and contributed to the development of key aspects of the Choose to Change intervention, including the letter, and clinical workflow. Because of this long-term partnership, we have established a system to ensure the successful coordination of research activities across all collaborating organizations. Specifically, the PIs and research managers from NNHSC, NU, and Alliance of Chicago biweekly during the EHR-system build and through project launch. Additionally, the Alliance research manager, project director (from NU), and Quitline manager meet once monthly to address any issues that arise regarding development, study implementation, and evaluation.

Setting

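### Secondary Aim 1 promises a comparison with usual care but defines an average cost per quit, which is not the cost of an additional quit

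*Combined protocol and SAP*

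**What the plan says.** Secondary Aim 1 (Cost Evaluation) has two parts. The first is a descriptive costing of therapy delivered through the letter-enhanced referral system. The second evaluates the cost-effectiveness of the letter and text messages "compared to usual care by calculation the cost-effectiveness ratio as the average dollars spent per successful quit".

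No formula with a between-arm difference appears in the text available for review, part of which had been removed. The Data Analysis section covers Primary Aims 1-3 and Exploratory Aims 1-2 and gives no cost method. Under Multiple Sites, one co-principal investigator "will be leading the cost evaluation component of the study", without a method.

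Other sections bear on the comparison:

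- Primary Aim 3 assumes CO-verified abstinence at 28 weeks of 7% in CtC and 2% in UC.
- On UC resource use, the section on Quitline treatment says: "Participants in both treatment conditions will have the opportunity to receive the same proactive Quitline treatment".
- On tracking in UC, the clinic workflow section says: "A different code, but unique to NNHSC, will be used to identify and track outcomes for Usual Care participants".
- On sessions, Treatment Outcomes says: "The frequency and duration of sessions will also be measured".
- On reporting, Data Analysis says: "Both raw and adjusted rates will be presented for each outcome by study condition".
- Under the alternative study timeline, people enrolled from February 2018 finish at week 14. Their abstinence is CO-verified then, not at week 28.

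**The concern.** A health system deciding whether to add the letter and texts to its current practice needs to know what one extra quit costs over that practice. UC is neither free nor without quits: its participants can receive free counseling and nicotine replacement, and 2% are expected to quit.

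The sentence can be followed in two ways:

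- **One ratio, for CtC.** UC costs and UC quits do not enter, so nothing is compared.
- **One ratio per arm.** The two averages contain the needed information if the quit rates are reported beside them, but neither is the cost of an additional quit. The reader would have to rebuild that figure and would have no measure of its uncertainty.

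Either way, the stated result does not answer the stated question.

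**Working it through.** **Inputs.** Quit rates of 7% (CtC) and 2% (UC) come from Primary Aim 3; 265 per arm, two-sided alpha 0.05 and stated power of 80% come from Power. The documents give no costs. Set CtC cost per participant to 1 and UC cost to r, and assume CtC costs at least as much as UC (r from 0 to 1).

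**Reproducing the plan's figure.** The plan states no cost figure, but the quit rates can be checked through the Aim 3 power. With pooled rate 0.045:

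- Null standard error = √(2 × 0.045 × 0.955 / 265) = 0.0180
- Alternative standard error = √((0.07 × 0.93 + 0.02 × 0.98) / 265) = 0.0179
- z = (0.05 − 1.96 × 0.0180) / 0.0179 = 0.82, so power is 79.5%, in line with the stated 80%.

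**Expected quits.** 265 × 0.07 = 18.55 in CtC and 265 × 0.02 = 5.30 in UC, so 13.25 are additional.

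**The ratios.**

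- CtC average = 1 / 0.07 = 14.29
- UC average = r / 0.02 = 50r
- Incremental = (1 − r) / (0.07 − 0.02) = 20(1 − r)
- Incremental / CtC average = 20(1 − r) × 0.07 = 1.4(1 − r)

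| r | CtC average | UC average | Incremental | Incremental / CtC average |
|---|---|---|---|---|
| 0 | 14.29 | 0 | 20.00 | 1.40 |
| 2/7 | 14.29 | 14.29 | 14.29 | 1.00 |
| 0.5 | 14.29 | 25.00 | 10.00 | 0.70 |
| 0.75 | 14.29 | 37.50 | 5.00 | 0.35 |
| 1 | 14.29 | 50.00 | 0 | 0 |

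The averages and the incremental ratio coincide only at r = 2/7. Below it, the CtC average understates the cost of an additional quit; above it, the CtC average overstates that cost.

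**In dollars (assumed, for illustration only).** At $50 for CtC and $10 for UC, the averages are $714 and $500 and an additional quit costs $40 / 0.05 = $800. At $50 and $20, the averages are $714 and $1,000 and an additional quit costs $30 / 0.05 = $600.

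**Rebuilding.** Incremental = 1.4 × CtC average − 0.4 × UC average. For the second case, 1.4 × 714.29 − 0.4 × 1,000 = 600.

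**Precision of the denominator.**

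- At 7% v 2%, 265 per arm: 0.0179 / 0.05 = 36% relative standard error; 95% interval 1.5 to 8.5 points.
- At the 3% v 10% that the Power section expects at 12 weeks: √((0.03 × 0.97 + 0.10 × 0.90) / 265) = 0.0212, and 0.0212 / 0.07 = 30%.
- At 7% v 2% with only half of each arm contributing (an assumed share): √(0.0847 / 132.5) = 0.0253, or 51%; 95% interval 0.04 to 10.0 points.

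**The case against.** The best defence is that the wording is loose, not wrong. The sentence speaks of one ratio and ties it to a comparator, so an incremental ratio may have been intended, and this is an aims statement rather than an analysis section. That may be so. But the text names an average, nothing else available corrects it, and the remedy is the same on either reading.

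The practical error may also be modest. If Quitline cost followed the planned engagement (10% v 24%) or utilization (7% v 15%), which is an assumption, r would be about 0.42 to 0.47. The incremental ratio would then be 1.4 × (1 − r), about 0.82 to 0.75 of the CtC average, and adding letter and text costs would lower r and bring the two closer. This is a fair caution about size, though it does not make the average the right quantity.

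Four stronger readings are tempting and are not supported:

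- **That the plan would report a misleading sign.** At r = 0.5 the CtC average minus the UC average is 14.3 − 25.0 = −10.7, while an additional quit costs +10.0. The plan never proposes subtracting the averages.
- **That the average flatters CtC.** Above r = 2/7 it works against CtC. Without costs, the direction is unknown.
- **That the incremental figure is lost.** Its point estimate can be rebuilt from arm-level costs and quit rates, if both are reported.
- **That 36% is the best attainable precision.** The plan's own 12-week rates give 30%. Nor are later enrollees' quits necessarily lost, since they are verified at week 14.

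**Conclusion.** The concern holds as a mismatch between a comparative objective and the statistic defined for it. At the planned 28-week rates, the cost of an additional quit is 1.4 × (1 − r) times the CtC average. This ranges from 1.4 times down to zero as r goes from 0 to 1, with equality at r = 2/7. The result rests on the planned rates and on CtC costing at least as much as UC. Where the trial falls in that range cannot be determined from the documents.

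This is a defect in one secondary definition and should be corrected before analysis. It does not touch the primary aims, the sample size or the descriptive cost analysis.

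**What to change.** Add to the analysis plan:

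1. **Statistic.** The comparative measure is the difference in mean cost per randomized participant (CtC minus UC) divided by the difference in intention-to-treat quit proportion, counting the same cost items in both arms.
2. **Quit and period.** State which verified quit enters the denominator: week 28 for the original timeline and week 14 for the shortened one, analysed separately or combined by a stated rule. Match the cost period to it.
3. **Uncertainty.** Bootstrap participants within arm and carry the cost and quit differences jointly, for example on a cost-effectiveness plane or as net benefit at stated values per quit. An interval for the ratio itself can be unstable when the quit difference is near zero.
4. **Descriptive.** Keep average cost per quit by arm under that label.

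The cost is a few sentences of text and a little more analysis, with no change to participant procedures. Quitline outcomes are already tracked in UC, session frequency and duration are measured, and dated clinic visits are extracted from the health record. These are utilization data, so UC unit costs are also needed on the same basis as CtC costs, which a comparison with usual care already implies. The downside is an imprecise result: the quit-rate difference has a relative standard error of about 36% at 7% v 2%, against √(0.07 × 0.93 / 265) / 0.07 = 22% for the CtC rate alone. It would be larger if fewer participants contribute.
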